#### Specific Aim 1b:

This aim will use clinical outcomes data from a previously recruited CITA cohort of 445 acamprosate-treated alcoholic patients and metabolomics data obtained with two metabolomics analytical platforms to identify metabolomic markers associated with length of sobriety as well as additional secondary phenotypes identified in Aim 1a. We will then apply a “pharmacometabolomics-informed pharmacogenomics” research strategy in which we will perform genome-wide association studies in search for genetic variants associated with metabolites associated with acamprosate clinical outcomes. We will pursue all signals, genes and pathways functionally and mechanistically in order to investigate the biological mechanisms underlying sobriety length and other phenotypes associated with acamprosate treatment response. This is the same approach that we used previously with success to study biological mechanisms contributing to effects of selective serotonin reuptake inhibitors in patients with major depressive disorder (MDD).

Specific Aim 2: To identify genetic and metabolomic biomarkers associated with acamprosate response in the new cohort of 800 alcoholic patients randomized to acamprosate or placebo treatment.

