#### Analysis for Specific Aim 1b

Metabolite concentrations will be log-2 transformed, and associations between baseline metabolite concentrations and the time of abstinence since baseline will be evaluated by linear regression with age and gender as covariates. If Timeline Follow Back (TLFB) data at 3-months is absent, the date of last contact will serve as the day of first lapse unless the subject has reported a lapse at an earlier time point. To study the possible effect of depression severity and liver function, regression models including baseline PHQ-9 scores and LFTs (AST, ALT, and GGT) will be compared with those without to determine whether the metabolites remain significantly correlated with treatment outcome. Participants who provided paired blood samples will be classified as responders (maintenance of complete abstinence) or non-responders (any consumption of alcoholic beverages during the trial period), and their metabolite concentrations at baseline and at 3 months will be compared by two-way ANOVA to detect any significant changes between the two time points and whether these changes differ significantly between groups.

After metabolomic markers associated with length of sobriety (or additional secondary phenotypes) are identified, we will apply a “pharmacometabolomics-informed pharmacogenomics” research strategy. Specifically, we will perform genome-wide association analyses to search for genetic variants associated with metabolites that are associated with acamprosate clinical outcomes. We will then evaluate the association of the identified genetic variants ( $p < 5 \times 10^{-8}$ ) with clinical treatment outcomes in all available datasets (including the COMBINE and PREDICT datasets used in Aim 1a). We will also pursue all signals, genes and pathways functionally and mechanistically in order to investigate the biological mechanisms underlying sobriety length and other phenotypes associated with acamprosate treatment response. This is the same approach that we used previously with success to study biological mechanisms contributing to effects of selective serotonin reuptake inhibitors in patients with major depressive disorder (MDD).

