#### Analysis for Specific Aim 2b:

Analysis for Aim 2b will use a similar strategy the analysis described above in aim 1b. However, in Aim 2b analyses will be performed on the much larger new sample and will also include assessment of drug interactions to evaluate whether metabolomics predictors of treatment outcome differ between acamprosate-treated and placebo-

treated patients. After identifying metabolites that predict treatment outcomes, we will again apply a pharmacometabolomics-informed pharmacogenomics analysis strategy, but genetic associations will be evaluated in the full sample of patients with genetic and treatment outcomes data, including the existing samples used in Aim 1 and the new samples collected in Aim 2.

Analysis for Specific Aim 3 will be completed in the future utilizing the latest methodology and analyses.

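### SNP-outcome p-values in Aims 1b and 2b that include the discovery patients are too small when the metabolite-outcome link arose by chance

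*Combined protocol and SAP*

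**What the plan says.** Aim 1b uses "clinical outcomes data from a previously recruited CITA cohort of 445 acamprosate-treated alcoholic patients" together with metabolomics on two platforms. The analysis section for that aim then sets out a chain of three steps.

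1. Metabolites are screened against outcome: "associations between baseline metabolite concentrations and the time of abstinence since baseline will be evaluated by linear regression with age and gender as covariates". No threshold is given for calling a metabolite associated.
2. The metabolites that pass go into "genome-wide association analyses to search for genetic variants associated with metabolites that are associated with acamprosate clinical outcomes", with p<5×10⁻⁸ as the cut for a variant.
3. The variants found are related to outcome "with clinical treatment outcomes in all available datasets (including the COMBINE and PREDICT datasets used in Aim 1a").

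Specific Aim 1a lists CITA as one of its three studies, alongside COMBINE and PREDICT. Nothing in the Aim 1b analysis removes CITA from step 3.

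Aim 2b repeats the strategy in the new trial and says "genetic associations will be evaluated in the full sample of patients with genetic and treatment outcomes data", explicitly counting both the Aim 1 samples and the new Aim 2 samples.

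For step 3 neither section states a significance level, whether datasets are pooled or reported one by one, a hold-out sample, or any adjustment for selection.

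**The concern.** The same CITA patients choose the metabolite through its correlation with outcome, choose the SNP through its correlation with that metabolite, and then supply data to the SNP-outcome test. If the metabolite-outcome correlation was a chance finding, that correlation has already been forced above a cut-off, and the SNP inherits a share of it. The SNP-outcome statistic is then no longer standard normal under the null.

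This step is what links a metabolite-related variant to treatment response, which is the declared purpose of the project. A p-value that includes the discovery patients would be read as evidence separate from the metabolite finding when it is only partly so.

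**Working it through.** The plan states no alpha, power or sample size for this step, so there is no figure of its own to reproduce.

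**Inputs from the documents**
- CITA: 443 patients (Table 2; Aim 1b says 445). 443 is used here.
- Acamprosate-treated patients, Table 2: 608 + 172 + 443 = 1,223; without CITA, 780.
- All patients, Table 2: 1,393 + 426 + 443 = 2,262. Aim 1a instead gives 1,687 for the three studies. The CITA share would then be 443/1,687 = 26%, so results fall between the two pooled rows below.
- SNP-metabolite cut p<5×10⁻⁸, two-sided z = 5.45. At n = 443 this needs an in-sample R² of at least z²/(z² + n − 2) = 29.7/(29.7 + 441) = 6.3% (about 6.5% using the t distribution). The SNP-metabolite correlation therefore cannot be negligible.

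**Assumptions (not in the documents)**
- Metabolite selected at two-sided p<0.05 or p<0.001.
- SNP-outcome test at two-sided 5%, with sample-size-weighted pooling.
- The same outcome in selection and testing.
- Metabolite and SNP both unrelated to outcome in truth.
- SNP R² of 7% to 30%.
- For Aim 2b, 533 new acamprosate patients (two thirds of 800, from the 2:1 notation).

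**Formula.** Let z_M be the metabolite-outcome statistic in the discovery cohort, with |z_M| > c, where c = 1.96 or 3.29. Let w be the discovery cohort's share of the test sample and ρ = √(R²·w). Under the null,

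z_SNP = ρ·z_M + √(1 − ρ²)·e, with e standard normal.

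Type I error is P(|z_SNP| > 1.96 given |z_M| > c).

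**One case in numbers.** With R² = 7% in CITA alone, ρ = 0.265. Selection at p<0.05 makes the mean |z_M| 2.34, so the SNP statistic is shifted on average by 0.265 × 2.34 = 0.62. At p<0.001 the mean |z_M| is 3.55 and the shift is 0.94. Pooled over 1,223, w = 443/1,223 = 0.362 and ρ falls to 0.159.

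**Type I error at nominal 5%, R² from 7% to 30%**

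| Test sample | w | Selection p<0.05 | Selection p<0.001 |
|---|---|---|---|
| CITA alone | 1 | 8.7-21.4% | 14.7-49.3% |
| Prior acamprosate patients, 443/1,223 | 0.362 | 6.3-10.8% | 8.4-20.3% |
| All prior patients, 443/2,262 | 0.196 | 5.7-8.1% | 6.9-13.1% |
| Aim 2b, new trial as discovery, acamprosate patients, 533/1,756 | 0.304 | 6.1-9.8% | 7.9-17.8% |
| Aim 2b, new trial as discovery, all patients, 800/3,062 | 0.261 | 6.0-9.1% | 7.5-15.9% |
| Aim 2b, CITA also used for selection, 976/1,756 | 0.556 | 7.1-13.9% | 10.3-29.0% |

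**Check on individual-level data.** A simulation of 443 CITA patients plus 780 independent patients (MAF 0.3 assumed, selection p<0.05, SNP R² of 6%, 10% and 20%) gave 9.1%, 10.7% and 16.0% in CITA alone, and 6.8%, 7.7% and 8.8% pooled. In COMBINE and PREDICT only it gave 5.4%, 5.0% and 5.2%. Leaving out the discovery cohort restores the nominal level.

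**Cost of leaving CITA out.** Approximate detectable log OR at 80% power and two-sided 5%, with one third abstinent: 2.80/√(N × (1/3)(2/3) × 2 × 0.3 × 0.7).
- N = 1,223: 2.80/10.68 = 0.262, OR about 1.30.
- N = 780: 2.80/8.53 = 0.328, OR about 1.39.

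**The case against.** Several objections have weight.

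- **Functional follow-up.** A reader might infer that false variants would pass this test and so reach the laboratory. The documents do not support that. The Aim 1b analysis says that all signals, genes and pathways will be pursued functionally, and does not make this conditional on the SNP-outcome result.
- **Role of the step.** A reader might also take it as a declared confirmation. The plan says only "We will then evaluate the association of the identified genetic variants" and claims no independent validation. The 5% level is therefore a yardstick chosen for this check.
- **Inclusion and pooling of CITA.** The parenthesis in Aim 1b names only the two cohorts not used for discovery, and pooling is not mentioned. If each cohort is reported separately, the COMBINE and PREDICT p-values are valid and only a label is missing. Still, the wording adds those two cohorts to a set from which CITA is not removed. In Aim 2b the overlap is explicit. The genetic associations there could be read as SNP-metabolite ones, but the sample is defined by having genetic and outcome data, which points to the SNP-outcome test.
- **Planned replication.** Aim 2b uses the same platforms in the new trial to replicate the Aim 1b metabolite results. That is an independent check on chance metabolites, and it lowers the stakes. It does not correct a SNP-outcome p-value that includes discovery patients.
- **Size.** The upper figures need a SNP explaining 30% of metabolite variance, and the documents give no such value. Selection uses abstinence time, while the primary outcome is yes/no sobriety. Testing a different outcome would weaken the carry-over. Under lenient selection and wide pooling the error is about 6%.

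The plan is exploratory and concedes low power for single SNPs. That makes the point modest without removing it.

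**Conclusion.** The point holds in limited form. Followed as written, the plan yields SNP-outcome p-values that are too small wherever discovery patients are in the test sample and the metabolite-outcome link is chance.

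Under the listed assumptions, with selection at p<0.05, type I error at a nominal 5% is about 9-21% in CITA alone, 6-11% over the 1,223 prior acamprosate patients and 6-8% over all 2,262. With selection at p<0.001 the ranges are about 15-49%, 8-20% and 7-13%. For Aim 2b with the new trial as the discovery set it is about 6-18% across both thresholds. The wider 7-29% applies only if CITA is also used for selection.

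All of these depend on a metabolite threshold, test level, pooling rule and SNP R² that the plan does not state. The damage is to the strength of the reported link between variants and treatment response. Results from COMBINE and PREDICT on their own are unaffected.

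**What to change.** In the analysis sections for Aims 1b and 2b, state that the SNP-outcome association is judged in cohorts that took no part in selecting the metabolite or the SNP:

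- **Aim 1b variants:** COMBINE and PREDICT, plus the new trial when available, provided the new trial was not itself used to decide which metabolites to keep.
- **Aim 2b variants:** COMBINE and PREDICT, plus CITA if it was not used for selection.

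Report discovery-cohort and pooled estimates separately and label them descriptive. In the same sentences give the metabolite selection threshold, the significance level for the SNP-outcome test and how cohorts are combined.

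The change is to SAP wording and needs no new data. Its downside is a smaller independent test: for Aim 1b, 780 instead of 1,223 prior acamprosate patients, with the detectable OR rising from about 1.30 to about 1.39 (MAF 0.3 assumed) before the new trial is added.

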#### Analysis for Specific Aim 2a

Genetic association analyses will evaluate the effect of SNP genotypes on acamprosate and placebo treatment outcomes. Well-established pipelines will be used for genotype quality control and imputation prior to performing the genetic association analyses. We will first perform genome-wide association analyses of the primary outcomes in the acamprosate-treated participants with available 3 month outcomes, using standard approaches. For example, we will evaluate the association of SNPs with 3 month continuous abstinence (yes/no) using logistic regression and with length of abstinence using Cox proportional hazard models. We will first use these models to evaluate the association of the treatment outcomes with covariates, including demographic and baseline clinical characteristics, such as depression and anxiety symptom severity (PHQ-9 and GAD-7 scores, respectively), and liver function tests (LFTs) – aspartate aminotransferase (AST), alanine transaminase (ALT) and Gamma-Glutamyltransferase (GGT). SNP association with the primary treatment outcomes will be evaluated while adjusting for relevant covariates and principal components derived from genome-wide SNP data to adjust for population stratification. As discussed in the Statistics Team Section, secondary analyses will also be performed using the entire sample of participants enrolled into the study [“intent-to-treat” (ITT) analysis]. If the same genetic variants contribute to lack of response in the “completer” group and to early dropout (which is likely the case as early dropout frequently results from relapse), the ITT analysis will have greater power than the “completer” analysis. We will also perform genome-wide association analyses using all participants (acamprosate and placebo), including a treatment covariate, and a SNP-treatment interaction to evaluate whether SNPs are associated with clinical outcomes in a drug-dependent manner (e.g. SNP is associated with acamprosate treatment outcome, but not placebo treatment outcome). We will

also evaluate the possibility of sex-specific genetic effects, or genetic effects that are modified by the presence of comorbidities such as depression and anxiety, by exploratory analyses involving interaction terms with these variables.

Most importantly, we will perform a genome-wide meta-analysis of acamprosate pharmacogenomics using the new data and data from available prior studies (COMBINE, PREDICT, CITA; see Aim 1).

Table 2 Subject Characteristics	COMBINE	PREDICT	CITA
N	1393	426	443
Age, mean(SD)	44.4 (10.2)	45.3 (8.7)	42.1 (11.8)
Sex, N(%) male	955 (69%)	328 (77%)	286 (65%)
Race, N(%) white non-Hispanic	1062 (77%)	426 (100%)	412 (93%)
Baseline Consumption Measures (last 30 days)			
Average drinks per drinking day	13.0 (8.1)	19.4 (11.3)	11.8 (7.7)
% drinking days	72.8 (23.5)	82.1 (1.3)	50.7 (29.7)
% heavy drinking days	65.2 (24.9)	79.0 (1.3)	45.8 (29.7)
Number of days since last drink	7.7 (5.3)	22.1 (4.4)	24.8 (16.1)
Medications			
Acamprosate, N	608	172	443
Naltrexone, N	614	169	0
No active drug (placebo or no medication), N	466	85	0
Treatment outcomes			
3 month abstinence from any drinking, N(%)	293 (21.2)	194 (45.5)	132 (29.7)
3 month abstinence from heavy drinking, N(%)	432 (31.2)	210 (49.3)	168 (37.9)

For COMBINE and CITA, baseline consumption is based on 30 days prior to the start of medication, while for PREDICT it is based on 30 days prior to the onset of inpatient treatment, as proposed by Mann and colleagues (84).

For the COMBINE study, the number of participants for each medication may include participants on more than one medication (i.e. groups are not mutually exclusive since the study included acamprosate/naltrexone co-treatment).

Numbers for treatment outcomes are based on the ITT sample (i.e. complete sample) assuming those who dropped out prior to 3 months had returned to heavy drinking.

As with the analysis described above, our meta-analyses will also include analyses of the full set of acamprosate and placebo treated participants, with a treatment covariate and tests of SNP-treatment interaction effects. However, our power estimate for the meta-analysis is based only on the combined sample of acamprosate-treated patients, since the size of this sample will determine the power to detect acamprosate-specific pharmacogenomics effects. Assuming a total sample of 1000 acamprosate-treated participants (ITT), the meta-analysis will provide 80% power to detect associations of SNPs with 3-month abstinence during acamprosate treatment (assume ~1/3 abstain and 2/3 relapse) with odds ratios of 2.07 and 1.80 for SNPs with minor allele frequencies (MAFs) of 0.2 and 0.4, respectively, at a genome-wide significance level of  $5 \times 10^{-8}$ . We also note that analyses of the full dataset (N≈1500) including participants that received acamprosate or other treatment options will provide greater power to detect genetic predictors of treatment-independent predictors of abstinence in patients with AUD.

We recognize that the available sample has relatively little power to detect the effects of individual SNPs, which tend to be very modest for complex traits such as alcohol-dependence related phenotypes. We will therefore apply more advanced analysis methods to maximize power of the study, including gene-level and pathway-based (gene-set) analyses using approaches such as MAGMA [42], and will evaluate polygenic risk score associations and AUD treatment outcomes.

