### **Resources:**

We will utilize substantial resources available at Mayo Clinic, such as the Clinical Research Unit (CRU), to support recruitment and proper specimen collection and procurement at the Mayo Health System sites. The addition of the large clinical operation at the Hazelden Betty Ford Foundation treatment facilities in Center City and Plymouth, MN will significantly increase the referral base allowing for a more rapid achievement of the recruitment targets; and trained personnel (in all research sites) enabling large-scale prescreening, selection, enrollment and monitoring of the study participants will be required to achieve this goal. Adding Hazelden St. Paul location will improve visit options for patient travel while participating in the study.

Genome-wide genotyping will be conducted by the Mayo Clinic 'Medical Genome Facility', which offers a variety of genotyping assays, including state-of-the-art genome-wide SNP arrays.

The amino acid metabolomic platform assays using the CITA samples will be performed at the Mayo Clinic Metabolomic Core Facility. During year 2, metabolomic assays for neuromodulator metabolites will be performed. The acamprosate placebo-controlled trial recruitment will continue throughout years 1, 2 and 3—with completion of the trial at the end of year 3.

The Statistics Team, which will be responsible for data management, biostatistics and bioinformatics support. The statistical team ([name], Postdoc, MS Statistician, and Statistical Programmer) will meet weekly to plan and review ongoing data analyses. [name], the Statistics Team Director and Co-PI for this study, obtained a PhD degree in biostatistics, with a focus on statistical genetics, followed by further training in statistical genetics as a postdoctoral research fellow. She joined Mayo Clinic's Program in Genomics of Addiction ten years ago.

(1a) This is a multisite study involving Mayo Clinic and non Mayo Clinic sites. *When checked, describe in detail the research procedures or activities that will be conducted by Mayo Clinic study staff.*

(1b) Mayo Clinic study staff will be engaged in research activity at a non Mayo Clinic site. *When checked, provide a detailed description of the activity that will be conducted by Mayo Clinic study staff.*

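### The lead Aim 2a scan, Cox model included, is limited to completers, so drinking data from months 1 and 2 can be left out of it, and its censoring and dropout rule is unwritten

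*Combined protocol and SAP*

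**What the plan says.** In Analysis for Specific Aim 2a, the first step is "genome-wide association analyses of the primary outcomes in the acamprosate-treated participants with available 3 month outcomes". Two example models follow: logistic regression for 3-month continuous abstinence, and SNP association "with length of abstinence using Cox proportional hazard models". The section later calls this the completer analysis and sets it against ITT: "As discussed in the Statistics Team Section, secondary analyses will also be performed using the entire sample of participants enrolled into the study". The only text on the Statistics Team is a staffing description under Resources ("The Statistics Team, which will be responsible for data management, biostatistics and bioinformatics support"), which contains no analysis rule.

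The Endpoints section defines the primary outcome as continuous sobriety over 3 months (yes/no). It lists days to first alcohol use by TLFB as a secondary outcome. It does not say how patients who leave early are handled.

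Table 1 schedules TLFB (or BDQ) at baseline and months 1, 2 and 3, but not at the telephone calls in weeks 2, 6 and 10.

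Dropout rules appear elsewhere:
- Aim 1b, for patients without a 3-month TLFB: "the date of last contact will serve as the day of first lapse unless the subject has reported a lapse", meaning one dated before that contact.
- Aim 2b: "Analysis for Aim 2b will use a similar strategy the analysis described above in aim 1b".
- Table 2, footnote 3, for the ITT counts of the three prior cohorts: "assuming those who dropped out prior to 3 months had returned to heavy drinking".

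The meta-analysis power statement assumes 1000 acamprosate-treated participants, counted as ITT.

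**The concern.** A lapse reported at month 1 or 2 already settles continuous sobriety as a no, and TLFB dates it. A patient who was sober at month 2 and then left has about 60 event-free days. A Cox model is built to use both kinds of record, and requiring a 3-month outcome can discard both.

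Two things are at stake. First, the lead scan can lose events and can become a scan of patients selected for staying, which matters if leaving is tied to relapse. Second, one dropout can carry different phenotypes across the plan: absent from the first Aim 2a scan, lapsed at last contact in Aim 2b if it follows Aim 1b, and returned to heavy drinking if the meta-analysis follows Table 2. The choice affects the result, so it should be fixed before the data are seen.

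**Working it through.** **1. How the text treats a patient who leaves before month 3**

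| Patient | First Aim 2a scan | Aim 2a ITT, new cohort | Aim 1b rule (Aim 2b if it follows) | Table 2, prior cohorts |
|---|---|---|---|---|
| Lapse reported at month 1 or 2, then left | Out, unless an available outcome includes a settled no | In; coding implied, not stated | Lapsed on reported day | Returned to heavy drinking |
| Sober at last visit, then left | Out | In; coding implied, not stated | Lapsed at last contact | Returned to heavy drinking |

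**2. The plan's own figure.** None is given for this scan. The nearest is the meta-analysis power: 80% for N = 1000 at alpha 5e-8. At MAF 0.2 and OR 2.07 it reproduces (78 to 79.5% by three tests). At MAF 0.4 and OR 1.80 it gives about 71% if exactly 1/3 abstain, and 78% if 40% abstain. Nothing below depends on it.

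**3. Inputs**
- From the documents: accrual 800; 2:1 allocation, so 800 × 2/3 ≈ 533 on acamprosate; about 1/3 abstinent; OR 2.07 at MAF 0.2; alpha 5e-8.
- Assumed: dropout d of 20/30/40%; exponential time to first drink with 1/3 lapse-free at day 90; leaving times uniform over days 0 to 90; drinking visits at days 30 and 60.

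**4. Events if dropout is unrelated to lapse**
- Completers: 533 × 2/3 × (1 − d) = 284 / 249 / 213.
- Lapse by day 30: 1 − (1/3)^(1/3) = 0.307. By day 60: 1 − (1/3)^(2/3) = 0.519.
- A dropout's last drinking visit is day 0, 30 or 60 with equal chance, so the probability of a recorded lapse is (0 + 0.307 + 0.519)/3 = 0.275.
- Extra events: 533 × 0.275 × d = 29 / 44 / 59.
- All follow-up: 314 / 293 / 272.

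**5. Events if every dropout reported a lapse and then left**
- All follow-up keeps 533 × 2/3 = 355 events.
- Completers keep 533 × (2/3 − d) = 249 / 195 / 142.
- Apparent abstinence among completers is (1/3)/(1 − d) = 42 / 48 / 56%, against a true 33%.

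**6. Strength of the Cox test.** This was simulated with N = 533, MAF 0.2, genotype hazards set to give OR 2.07 for 3-month abstinence, and 2500 to 3000 runs per cell. With no dropout the HR is 0.63, mean chi-square 21.0 and power 0.15. The table gives mean chi-square at 20/30/40% dropout, with HR in brackets where computed.

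| Dropouts | Completers | All, censored at last drinking visit | All, lapse at last contact |
|---|---|---|---|
| Unrelated to lapse | 17.0/15.0/13.0 (0.63) | 18.6/17.4/16.4 (0.63) | 15.2/13.0/10.8 (0.70/0.73/0.75) |
| All left after a reported lapse | 17.3/14.8/11.4 | about 21 | about 21 |
| Half left on an unreported lapse | 17.6/15.8/13.6 | 17.6/15.8/13.7 | 18.3/17.1/15.1* |
| All left on an unreported lapse | 18.0/15.9/13.4 (0.60/0.58/0.56) | 16.3/13.5/10.6 (0.62/0.61/0.60) | 20.5/19.7/18.9 |

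*A separate run of 1500 per cell, taking last contact as the leaving date.

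With unrelated dropout, power at 5e-8 is 0.061/0.037/0.012 for completers and 0.094/0.063/0.048 with censoring. It is about 15% or less in every version. Reversing the allele direction gives the same pattern for completers against censoring.

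**The case against.** The strongest reply is that little is actually lost.

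- **ITT is planned.** These patients are missing from the first scan only. Their coding is also implied. The section argues that ITT gains power when the same variants drive non-response and early dropout, which makes sense only if dropouts count as non-responders. Table 2 footnote 3 uses that convention. This stands; what is missing is a written statement for the new cohort.
- **The event is inferable.** First alcohol use is a listed secondary outcome, and a true completer set with drinking recorded to month 3 needs no dropout rule. This stands too. The gap is in censoring and dropout handling once other patients are included.
- **An available 3-month outcome may already include a reported lapse.** The wording allows this, although the completer label points the other way. If so, the logistic change only confirms the intent, and the Cox gain shrinks to the sober follow-up.
- **Censoring is not neutral.** The plan itself says early dropout often results from relapse. The last row of the table shows censoring can then be weaker than the completer scan.
- **The consequence is small.** Cox is offered as an example, length of abstinence is a secondary outcome, and Limitations concedes that this cohort alone is unlikely to have enough power.

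A reader might infer that the plan discards these data altogether, lacks any event definition, or should adopt censoring or put ITT first. The documents do not support any of these. The first two fail on the planned ITT analysis and the Endpoints section. The third depends on the share of dropouts who left on an unreported lapse, which the documents do not give.

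**Conclusion.** The point holds as a minor one. The restriction to available 3-month outcomes, read as the completer group, excludes recorded lapses and sober time from the lead scan for no stated reason, and the rule for patients who leave is not written for this cohort.

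Under assumed dropout of 20/30/40% unrelated to lapse, the difference is 30, 44 or 59 events. If dropouts leave after a reported lapse, it is larger and the completer set looks too abstinent. If most leave on an unreported lapse, censoring does not help the test, although its HR stays nearer the true 0.63 than the completer HR does. The break-even in chi-square between censoring and completers is at about half of dropouts. These sizes rest on the assumed dropout, exponential lapse times and uniform leaving times.

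The gain is retained data, less selection on completion and one phenotype across analyses. It is not adequate power for a single-cohort scan.

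**What to change.** 1. **Cox scan.** Include every acamprosate-treated patient with any follow-up drinking data, and count each reported lapse as an event on its reported date. For patients who left with no reported lapse, pre-specify two versions: censored at the last day covered by TLFB or BDQ, and lapse at last contact as in Aim 1b. Name in advance which one leads. Say whether a telephone call without TLFB counts as last contact.
2. **Logistic scan.** State that any reported lapse makes the patient not continuously sober, whether or not the 3-month visit took place.
3. **Meta-analysis.** Confirm that the new cohort's dropouts enter the ITT analysis with the Table 2 footnote 3 coding, and replace the pointer to the Statistics Team Section with that rule.

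The cost is a few sentences and one extra Cox run, with no new data. Item 2 barely moves the logistic estimate: with unrelated dropout the OR goes from 2.07 to 2.08/2.09/2.10. The downside is that censoring may be informative, and the censored version can then be weaker than the completer one. Lapse at last contact dilutes the HR if dropout is unrelated to lapse. Reporting both versions shows how much the choice matters.
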